7.8. Vital Signs

Vital signs, including measurement of systolic and diastolic blood pressure, pulse, heart rate, and O₂ saturation, are to be measured in the sitting position as per the schedule of events (Appendix A). At dosing visits, vital signs will be measured pre-dose as well as 1 hour post-dose and entered into the eCRF. Vitals signs should be monitored every 15 minutes during the infusion and captured on the source document.

If a vital sign abnormality is considered by the Investigator to be clinically significant, then the abnormality is to be recorded as part of the subject's medical history if occurring prior to start of dosing and as an AE occurring if after the start of study drug administration at Week 0, where the finding represents a change from Baseline.

7.9. Concurrent Medications

All prescription and non-prescription medications including pharmacologic doses of vitamins, herbal medicines, or other non-traditional medicines, taken from 4 weeks prior to the first dose of PRM-151 through the last study visit must be recorded in the eCRF.

If on pirfenidone or nintedanib, subject must have been on a stable dose of pirfenidone or nintedanib for at least 3 months prior to screening without increase in FVC% predicted on two consecutive PFTs, including screening PFTs. If subjects are currently on a stable dose of pirfenidone they are allowed to stop taking pirfenidone while remaining in the study but are not allowed to start dosing with nintedanib. If subjects are currently on a stable dose of nintedanib they are allowed to stop taking nintedanib while remaining in the study but are not allowed to start dosing with pirfenidone.

7.9.1. Prohibited Concurrent Medications

The following medications are prohibited during the study:

- All investigational therapies other than PRM-151 for any indication, including therapies that are approved in other indications that are being investigated in IPF, are prohibited within 4 weeks before Screening and during study participation.
- Inhaled or systemic corticosteroids. (Low dose [≤ 10 mg daily] corticosteroids are permissible, provided the dose has been stable for 30 days prior to Baseline.)
- Bronchodilators:
 - Short-acting bronchodilator use within 12 hours of pulmonary function, DLco, and 6MWT assessments.
 - Long acting bronchodilators are disallowed the day of and within 24 hours of pulmonary function testing, DLco, and 6MWT assessments.
- The use of inhaled bronchodilator agents at times outside these windows is permissible.
- Immuno-suppressants (e.g. methotrexate, azathioprine, cyclophosphamide, cyclosporine, everolimus or other immunosuppressants including those used after organ transplant) are prohibited within 4 weeks of baseline and during the study.

7.10. Efficacy Measurements

On all dosing days, dosing will occur after all safety and efficacy assessments scheduled for that visit are complete.

7.10.1. Pulmonary Function Tests

Spirometry will be measured according to ATS guidelines (Miller, Crapo et al. 2005a), as per the schedule of events (Appendix A).

DL_{CO} is to be measured using the single-breath technique according to ATS/ERS guidelines (MacIntyre, Crapo et al. 2005) at Screening, Baseline and at Week 28, and weeks 76 and 128 visits for subjects continuing treatment in the extension. Diffusion capacity should be done on the same day as HRCT.

Lung volumes (TLC and FRC) using Nitrogen washout method (Wanger, Clausen et al. 2005) will be performed at Screening, Baseline and Week 28, and weeks 76 and 128 visits for subjects continuing treatment in the extension.

PFTs will be reviewed centrally by reviewers blinded to treatment group and time point.

7.10.2. Six-minute Walk Test

Exercise tolerance will be evaluate during the 6MWT according to ATS guidelines (ATS 2002) (Appendix B) as per the schedule of events (Appendix A). If possible, 6MWT

should be the last efficacy assessment completed, by the subject. If it is not possible to complete the 6MWT last, then allow a 30-minute recovery time before continuing with the next efficacy assessment. During the open-labeled extension, subjects will have 6MWT measured every twelve weeks.

7.10.3. **High-resolution Computed Tomography**

High-resolution Computed Tomography (HRCT) will be performed at the Baseline and Weeks 28, and weeks 76 and 128 visits for subjects continuing treatment in the extension.

Spirometry will be performed at selected sites to ensure that full inspiration HRCT is at Total Lung Capacity (TLC).

HRCT is to be performed with the subject in the supine position and at full inspiration. Contiguous CT volumetric acquisition will be obtained according to a specified protocol. HRCT scans will be compared using a standardized reading protocol and software to assess treatment-related changes in lung fibrosis.

7.10.4. **Patient Reported Outcomes**

Kings Brief Interstitial Lung Disease questionnaire (K-BILD) (Patel, Siegert et al.) (Appendix D) is a disease specific questionnaire validated to look at the health status of subjects with a variety of forms of interstitial lung disease (ILD). It consists of 15 items. The K-BILD questionnaire will be performed as per the schedule of events (Appendix A). If possible, the questionnaire should be the first assessment completed by the subjects.

Leicester Cough Questionnaire (Birring, Prudon et al. 2003) (Appendix E) a self-completed health related quality of life measure of chronic cough. The LCQ total score ranges from 3 to 21 and from 1 to 7 for physical, psychological and social domains; a higher score indicates a better health-related quality of life. The LCQ questionnaire will be performed as per the schedule of events (Appendix A). If possible, the questionnaire should be the first assessment completed by the subjects.

7.10.5. **Pentraxin-2 Levels**

Blood samples for determination of pentraxin-2 levels are to be collected pre-dose as per the schedule of events (Appendix A).

7.10.6. **Anti-Pentraxin 2 antibodies / Anti-Drug Antibodies (ADA)**

Blood samples for determination of ADA levels are to be collected pre-dose as per the schedule of events (Appendix A).

7.11. **Biomarker Assessments**

7.11.1. **Baseline Genetic Status**

The subject's baseline genetic status for TLR3, L412F polymorphism, and MUC5B promoter polymorphism will be collected at Baseline, if available. If the subject has not previously been tested for these genetic characteristics, a blood sample for this analysis should be drawn at baseline.

7.11.2. **Blood Sample Collection for Biomarker Assessment**

Blood samples to study exploratory serum and cellular biomarkers are to be collected pre-dose at Baseline, Week 28 and at Week 128 of the open label extension.

7.12. **Safety Measurements**

7.12.1. **Adverse Events**

An AE is any untoward medical occurrence in a subject administered a pharmaceutical product and that does not necessarily have a causal relationship with this treatment. An AE can therefore be any unfavorable and unintended sign (including an abnormal laboratory finding), symptom, or disease temporally associated with the use of study drug, whether or not related to study drug.

All AEs from signing of informed consent until last study visit will be entered in the database. For those subjects prematurely withdrawn, TEAEs will be monitored until, at least, 4 weeks from last study treatment dose or resolution of AE, whichever is earlier

7.12.1.1. **Respiratory Decline Events**

For the purposes of this study, such “respiratory decline” events are defined as follows:

- Unscheduled visits to a healthcare professional for respiratory status deterioration.
- Urgent care visits for respiratory status deterioration.
- Hospitalization due to a worsening or exacerbation of respiratory symptoms.

All “respiratory decline” events will be further characterized according to the definitions of IPF-related acute exacerbation, as proposed by an expert committee sponsored by the IPF Clinical Research Network and the National Heart Lung and Blood Institute (NHLBI) (Collard, Moore et al. 2007) and applied by (Collard, Yow et al. 2013)

- Acute onset of symptoms (< 30 days in duration)
- New radiographic abnormalities (bilateral ground glass or consolidation on HRCT with no pneumothorax or pleural effusion)
- The absence of an identified infectious etiology by routine clinical practice
- Exclusion of alternative causes by routine clinical practice including:
 - a. Left heart failure
 - b. Pulmonary embolism
 - c. Identifiable cause of acute lung injury

7.12.1.2. **Infusion related reactions**

In the event of acute hypersensitivity or other infusion reaction, institutional protocol should be initiated, ECG should be performed, and a blood sample drawn for cytokines. Signs and symptoms of an infusion reaction may include the following: headache, fever, facial flushing, pruritis, myalgia, nausea, chest tightness, dyspnea, vomiting, erythema, abdominal discomfort, diaphoresis, shivers, hypertension, hypotension, lightheadedness, palpitations, urticaria and somnolence. Although unlikely, serious allergic reactions (e.g., anaphylaxis) may occur at any time during the infusion.

In the case of Grade 2 occurrence of signs and symptoms consistent with infusion related reaction, follow institutional protocol and reduce the rate of infusion of PRM-151 to half the initial rate; consider discontinue infusion of PRM-151 if symptoms do not respond to medical intervention. If signs and symptoms resolve with intervention including discontinuation of PRM-151, PRM-151 infusion may be restarted at half the initial rate.

In the case of Grade 3 or greater occurrence of signs and symptoms consistent with infusion related reaction, discontinue infusion of PRM-151.

In the event of an infusion related reactions, an ECG should be performed and a blood sample for cytokines should be collected as soon as possible after stabilization of the subject.

If PRM-151 resulted in signs and symptoms consistent with Grade 2 or 3 Infusion related reaction, infuse PRM-151 over 120 minutes and use the following premedication for all subsequent PRM-151 administration:

- Diphenhydramine 50 mg IV or clemastine 2 mg IV (or an equivalent dose of an antihistaminic drug)
- Dexamethasone 10 mg IV (or an equivalent dose of a long acting corticosteroid)

Infusion related reactions must be reported to Promedior as described in section 7.12.4.1, Reporting of Adverse Events of Special Interest.

7.12.1.3. Adverse Drug Reaction

A suspected adverse drug reaction (ADR) is any AE for which there is a reasonable possibility that the drug caused the AE. For the purposes of Health Authority safety reporting, ‘reasonable possibility’ means there is evidence to suggest a causal relationship between the drug and the AE. A suspected adverse reaction implies a lesser degree of certainty about causality than adverse reaction, which means any AE caused by a drug.

7.12.1.4. Unexpected Adverse Event

An unexpected AE or suspected adverse reaction is considered “unexpected” if it is not listed in the Investigator Brochure or is not listed at the specificity or severity that has been observed; or, if an Investigator Brochure is not required or available, is not consistent with the risk information described in the general investigational plan or elsewhere in the current application, as amended.

7.12.1.5. Serious Adverse Event

An AE or suspected ADR is considered “serious” if, in the view of either the Investigator or Sponsor, it results in any of the following outcomes:

- Death.
- A life-threatening AE. Life-threatening means that the subject was at immediate risk of death from the reaction as it occurred, i.e., it does not include a reaction

which hypothetically might have caused death had it occurred in a more severe form.

- In-subject hospitalization or prolongation of existing hospitalization. Hospitalization admissions and/or surgical operations scheduled to occur during the study period, but planned prior to study entry are not considered AEs if the illness or disease existed before the subject was enrolled in the study, provided that it did not deteriorate in an unexpected manner during the study (e.g., surgery performed earlier than planned).
- Persistent or significant disability/incapacity or substantial disruption of the ability to conduct normal life functions.
- Is a congenital anomaly/birth defect.

An important medical event that may not result in death, be life-threatening, or require hospitalization may be considered serious when, based upon appropriate medical judgment, it may jeopardize the subject or may require medical or surgical intervention to prevent one of the outcomes listed in the definitions for SAEs. Examples of such medical events include allergic bronchospasm requiring intensive treatment in an emergency room or at home, blood dyscrasias or convulsions that do not result in -subject hospitalization, or the development of drug dependency or drug abuse.

7.12.2. Adverse Event Assessment

All AEs from signing of informed consent until last study visit will be entered in the database, but only AEs occurred from the time of first study treatment dose administered to the subject (TEAEs) until last study visit will be analysed (see 7.12.1). This includes AEs the subject reports spontaneously, those observed by the Investigator, and those elicited by the Investigator in response to open-ended questions during scheduled study center visits.

Each AE is to be assessed by the Investigator with regard to the following categories.

Serious/Non-Serious

Adverse events that meet the criteria specified above are to be considered serious.

Relationship to Study Drug

Relationship of an AE or SAE to investigational product is to be determined by the Investigator based on the definitions in Table 7-1.

Table 7-1: Adverse Event Relatedness

Relationship to Study Drug	Definition
Not Related	Unrelated to investigational product
Possibly Related	A clinical event or laboratory abnormality with a reasonable time sequence to administration of investigational product, but which could also be explained by concurrent disease or other drugs or chemicals.
Probably Related	A clinical event or laboratory abnormality with a reasonable time sequence to administration of investigational product, unlikely to be attributable to concurrent disease or other drugs and chemicals and which follows a clinically reasonable response on de-challenge. The association of the clinical event or laboratory abnormality must also have some biologic plausibility, at least on theoretical grounds.

Intensity

The Investigator is to determine the intensity of the AE according to the criteria in Table 7-2.

Table 7-2: Adverse Event Grading

Severity	Definition
Grade 1 (Mild):	Mild; asymptomatic or mild symptoms; clinical or diagnostic observations only; intervention not indicated.
Grade 2 (Moderate):	Moderate; minimal, local or noninvasive intervention indicated; limiting age-appropriate instrumental ADL.
Grade 3 (Severe):	Severe or medically significant but not immediately life-threatening; hospitalization or prolongation of hospitalization indicated; disabling; limiting self-care ADL.
Grade 4 (Life-threatening):	Life-threatening consequences; urgent intervention indicated.
Grade 5 (Death):	Death related to AE.

7.12.3. Recording Adverse Events

Only TEAEs will be recorded (see 7.12.1). All AEs, regardless of relationship to study drug, are to be recorded in the Adverse Events eCRF. All AE reports are to contain the

following details regarding the AE: a brief description, onset date, duration, intensity, treatment required, relationship to study drug, study drug action taken, outcome, and whether the event is classified as serious.

7.12.4. Reporting Serious Adverse Events

Only serious TEAEs will be recorded (see 7.12.1). The Investigator must report all SAEs to the Safety Unit [REDACTED] within 24 hours of discovery either by e-mail or fax to:

- [REDACTED]
- [REDACTED]
- [REDACTED]

A completed SAE report is to be sent to [REDACTED] Safety Unit within 24 hours of discovering the event. The initial report should include at least the following information:

- Subject's study number;
- Description and date of the event;
- Criterion for serious; and
- Preliminary assignment of causality to study drug.

The Safety unit will contact the Investigator either by email or telephone for follow-up information regarding the SAE, as appropriate.

7.12.4.1. Reporting Adverse Events of Special Interest

The Investigator must report suspected Infusion Related Reaction, regardless of severity, on an Adverse Event of Special Interest (AESI) form. This form must be completed and submitted, either by e-mail or fax to [REDACTED] Drug Safety Unit, immediately but no later than 24 hours of the Investigator's learning of the event to [REDACTED] Safety Unit:

- [REDACTED]
- [REDACTED]
- [REDACTED]

7.12.4.2. Follow-Up of Adverse Events

The Investigator must continue to follow all SAEs and non-serious AEs considered to be reasonably or possibly related to study drug either until resolution or the Investigator assesses them as chronic or stable. This follow-up may extend after the end of the study.

7.12.4.3. Reporting Safety Information

The Investigator must promptly report to his or her IRB/EC all unanticipated problems involving risks to subjects. This includes death from any cause and all SAEs reasonably or possibly associated with the use of study drug according to the IRB/EC's procedures.

8. STATISTICAL ANALYSES

8.1. Statistical Basis for Sample Size

The primary objective is not to formally demonstrate the superiority of PRM-151 over placebo, but to provide a reliable estimate of the size of the effect of PRM-151 on absolute change from baseline to 28 weeks in mean FVC% predicted, hereafter referred to as the primary endpoint. Nevertheless, the sample-size has been calculated to ensure a sufficient power to demonstrate the efficacy of PRM-151 over placebo on the primary endpoint under a set of hypotheses on effect sizes in the two groups and on the variability of the primary endpoint.

The primary endpoint will be tested in a model with two types of subjects: subjects on a stable dose of pirfenidone or nintedanib, and subjects not on other treatment for IPF.

The sample size calculation is based on the following assumptions:

- Primary endpoint is normally distributed
- Homogeneity of variance, i.e. the standard deviation is the same in both arms, and for both types of subjects.
- Randomization ratio PRM-151: placebo equals 2:1.
- Expected value of the primary endpoint for subjects on pirfenidone or nintedanib will be -1.5.
- Expected value of the primary endpoint for subjects on no other treatment will be -3.
- Expected value of the primary endpoint for subjects on PRM-151 will be ≥ 0.75 .
- Standard deviation of the primary endpoint is 5
- 75% of subjects will be on a stable dose of pirfenidone or nintedanib
- 25% of subjects will not be on other treatment for IPF
- Significance level (α)=0.10 two-sided.
- Desired power to demonstrate superiority is 80%

A sample size of one hundred and two (102) evaluable subjects in total (68 PRM-151 and 34 placebo) is enough to demonstrate superiority at $p < 0.10$ with a power of 80% under the above assumptions. Assuming a non-evaluability rate of about 15%, 117 subjects in total (78 PRM-151 and 39 placebo) are to be enrolled. Stratified randomization will ensure a balance of PRM-151: placebo in subjects on pirfenidone or nintedanib and not on any other therapy, with at least 25% of subjects on no other therapy.

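### 117 enrolled with about 15% non-evaluable leaves about 99 evaluable subjects rather than 102; 117 supports 102 only at about 13% loss, a difference of about one power point

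*Protocol*

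**What the plan says.** Protocol section 8.1 lists the design assumptions:

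- Error rate: "Significance level (α)=0.10 two-sided".
- Power: "Desired power to demonstrate superiority is 80" percent.
- Without PRM-151, background-therapy stratum: "Expected value of the primary endpoint for subjects on pirfenidone or nintedanib will be -1.5".
- Without PRM-151, untreated stratum: "Expected value of the primary endpoint for subjects on no other treatment will be -3".
- Active arm: "Expected value of the primary endpoint for subjects on PRM-151 will be" at least 0.75.
- Stratum mix: "75% of subjects will be on a stable dose of pirfenidone or nintedanib" and "25% of subjects will not be on other treatment for IPF".
- Standard deviation 5 and 2:1 allocation.

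From these it derives 102 evaluable subjects, 68 on PRM-151 and 34 on placebo. The enrolment target follows in one sentence: "Assuming a non-evaluability rate of about 15%, 117 subjects in total (78 PRM-151 and 39 placebo) are to be enrolled".

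The same 102, 15% and 117 appear under Sample Size Considerations in the protocol synopsis and in SAP section 2.3.2. None of the three places gives the inflation formula or says what makes a subject non-evaluable.

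**The concern.** A non-evaluability rate is normally read as a share of those enrolled. On that reading, losing 15% of 117 leaves fewer than the 102 subjects on which the stated power rests, so the enrolment target does not follow from the plan's own loss rate.

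What is at stake is the traceability of the sample-size justification more than the trial's ability to answer its question. The sentence stands in both documents and would probably pass into the study report, where a reader can see the mismatch with one multiplication. It also leaves unclear how much loss the design was meant to absorb.

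**Working it through.** **Inputs** (Protocol 8.1): means without PRM-151 of −1.5 (75% of subjects) and −3 (25%); PRM-151 mean 0.75, the lower limit of the stated range; SD 5; two-sided α = 0.10; power 80%; allocation 2:1; loss 15%.

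**Step 1: reproduce 102.**

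- Pooled placebo mean: 0.75 × (−1.5) + 0.25 × (−3) = −1.875.
- Difference: 0.75 − (−1.875) = 2.625.
- With 2:1 allocation, placebo n = (1 + 1/2) × [SD × (z₀.₉₅ + z₀.₈₀) / difference]² = 1.5 × [5 × (1.645 + 0.842) / 2.625]² = 33.65, rounded up to 34.
- PRM-151 n = 68, total 102. This matches the plan.

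Other settings do not fit: one-sided α = 0.10 gives 75 in total, and two-sided α = 0.05 gives 129.

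**Step 2: apply the loss rate to 117.**

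- Total: 117 × 0.85 = 99.45.
- By arm: 78 × 0.85 = 66.3 and 39 × 0.85 = 33.15, so about 66 + 33 = 99.
- Loss at which 117 still leaves 102: (117 − 102)/117 = 15/117 = 12.8%.
- Enrolment needed for 102 at 15% loss: 102/0.85 = 120 (80 + 40).

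**Step 3: how 117 could arise.**

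- 102 × 1.15 = 117.3. By arm, 68 × 1.15 = 78.2 and 34 × 1.15 = 39.1, which round to the stated 78 and 39.
- Equivalently, 15 extra subjects against a base of 102 is 15/102 = 14.7%.
- Both routes measure the loss against the evaluable number instead of the enrolled number. The documents do not say which, if either, was used.

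**Step 4: effect on power.**

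Normal approximation: power = Φ(difference/SE − 1.645), with SE = 5 × √(1/n₁ + 1/n₂). The noncentral t figures use N − 3 degrees of freedom, for the model with treatment and stratum.

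| Evaluable | SE | Normal | Noncentral t |
|---|---|---|---|
| 68 + 34 = 102 | 1.050 | 80.4% | 79.9% |
| 66 + 33 = 99 | 1.066 | 79.3% | 78.8% |
| 78 + 39 = 117 (no loss) | 0.981 | 84.9% | 84.5% |

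The shortfall costs 80.4 − 79.3 = 1.1 points. The half-width of the 90% confidence interval moves from 1.645 × 1.050 = 1.73 to 1.645 × 1.066 = 1.75 percentage points of FVC % predicted.

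**The case against.** Four points can be made for the plan.

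**The figures are approximate.** The loss is given as about 15%, and the study-design sections (protocol synopsis, Protocol 4.1, SAP 2.3.1) describe enrolment as approximately 117. A reader might infer that the three figures flatly contradict one another. The documents do not support that: 12.8% rounded to the nearest 5% is 15%, and 120 against 117 is a difference of 3/117 = 2.6%. What remains is that the rest of the calculation is exact to the subject, and the rate that fits 117 would ordinarily be called about 13%.

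**The cause is not documented.** A reader might take it as established that 102 was multiplied by 1.15 by mistake. With no formula printed, that is an inference. The mismatch does not depend on it, because 117 × 0.85 is below 102 however 117 was reached.

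**99 is not a forecast of the primary-analysis sample.** A reader might infer that the trial will analyse 99 subjects and be underpowered. Non-evaluable is never defined. Protocol 8.4 and 8.5.1.1 keep any treated subject with one post-baseline FVC and carry the last value forward. SAP 3.2, 5.2.5.1 and 6.1 move to all treated subjects and a mixed model using every available visit from Week 4 to Week 28. Most subjects who miss only Week 28 therefore still contribute. This stands as a limit on the consequence, but it does not repair the sentence: the plan itself assumes about 15% are non-evaluable, and SAP 2.3.2 keeps that assumption after the change of population and model.

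**Little depends on it.** The stated objective is estimation rather than a formal demonstration of superiority, and 0.75 is the lower limit of the assumed active-arm mean. Choosing the t over the normal calculation at 102 already moves power by half a point (80.4% to 79.9%). All of this stands, and it is why the point is editorial.

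**Conclusion.** The point holds as a minor inconsistency in the sample-size justification. Taken at 15%, the stated loss leaves about 99 evaluable subjects from 117; the 102 needs a loss of no more than 12.8%. The cost is about three subjects and about one power point (79.3% against 80.4%).

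This rests on reading the rate as a share of those enrolled, on equal loss in the two arms, and on the stated means, SD and stratum mix. The power figures belong to the two-group comparison of Week 28 change used for sizing. They are not the power of the SAP's mixed model, for which the documents give no variance components. The finding does not show that the trial is materially underpowered, and it gives no reason to change the enrolment target.

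**What to change.** Keep 117 and change the loss allowance in the protocol synopsis, Protocol 8.1 and SAP 2.3.2 to: *allows for about 13% non-evaluable (102 of 117)*. This is the safer wording, because it introduces no new power figure for an analysis that the SAP no longer treats as primary.

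If 15% is to stay, say instead that it leaves about 99 evaluable subjects and about 79% power under the calculation based on Week 28 change. Whichever is chosen, a few words on what counts as non-evaluable would help, given how both documents treat a missing Week 28 value.

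The cost is one sentence, repeated in three places. Conduct, analysis and error rate do not change. The only loss is that the stated allowance looks slightly less generous.
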